4.1.4 Drug assignment and administration of doses for each subject

The investigator (or authorised designee) will administer the trial medication as an [REDACTED] together with about 240 mL of water to subjects who are in an upright position. The so-called four-eye principle (two-person rule) should be applied for administrations: 1 authorised employee of the trial site should witness the administration of trial medication, and – if applicable – its preparation (e.g. reconstitution), if correct dosage cannot be ensured otherwise.

During the first 4 h after drug administration, subjects are not allowed to lie down (i.e. no declination of the upper body of more than 45 degrees from upright posture except for medical examination) or to sleep.

Subjects will be kept under close medical surveillance for at least 24 hours after drug administration (SRD and FE part).

For restrictions with regard to diet, see Section [4.2.2.2](#).

SRD part

The treatments to be evaluated in the SRD part are outlined in Table [4.1.4: 1](#) below. The dose volume for placebo corresponds to the dose volume of the corresponding dose level.

Administration of trial medication will be performed after subjects have fasted overnight; fasting is to start no later than 10 h before the scheduled dosing.

Table 4.1.4: 1 BI 3000202 and placebo treatments in SRD part

Dose group	Substance
1	BI 3000202
2	BI 3000202
3	BI 3000202
4	BI 3000202
5	BI 3000202
6	BI 3000202
7	BI 3000202
1-7	Placebo*

* Subjects receiving pl

FE part

Table 4.1.4: 2

Treatment	Substance
R	BI 3000202
T	BI 3000202

For treatment T, a high-fat, high-calorie meal will be served 30 min before drug administration. The subjects must completely consume the meal prior to drug intake. The composition of the standard high-fat, high-calorie meal is detailed in Table 4.1.4: 3; this meal is in compliance with the FDA guidance 'Food-Effect Bioavailability and Fed Bioequivalence Studies' ([R03-2269](#)).

Table 4.1.4: 3 Composition of the high-fat, high-calorie meal

Ingredients	kcal
2 chicken eggs (whole content) for scrambled eggs	192
10 g butter for frying scrambled eggs	75
35 g fried bacon	186
2 toasted slices of wheat bread	130
15 g butter for buttering toast slices	113
115 g hash brown potatoes	132
240 mL whole milk (3.5% fat)	156
Sum ¹	984

¹ The total caloric content was supplied approximately as following: 150 kcal as protein, 250 kcal as carbohydrate, and 500 to 600 kcal as fat.

For treatment R, administration of trial medication will be performed after subjects have fasted overnight; fasting is to start no later than 10 h before the scheduled dosing.

For restrictions with regard to diet, see Section [4.2.2.2](#).

4.1.5 Blinding and procedures for unblinding

4.1.5.1 Blinding

The table below summarizes the masking/blinding level of individual functions, roles and responsibilities involved in the trial.

Table 4.1.5.1: 1 Blinding level of individual functions

Role/function	Timing of Unblinding / receiving access to the treatment information (including rationale)
Subject/Participant	SRD part This trial part is blinded to treatment but not to dose level. The dose level will be known to the subject/participant. FE part This open label trial part will provide the subject treatment information as soon as treatment has been assigned.
Investigator/Site Staff	As requested to prepare trial site prior to first subject entered. The randomisation scheme will be provided to the trial site prior to randomisation for preparation of medication.
Sponsor trial team and data	As requested during trial conduct.
Bioanalytical Staff	As requested for analysis of bioanalytical samples.
Pharmacologist/ Biomarker expert/ Pharmacometrician	As requested for preliminary, interim analysis of pharmacokinetic, pharmacodynamic data or pharmacometric modelling.
Drug metabolism scientist	As requested for analysis of drug metabolites.
ECG laboratory	Within the central ECG lab, the staff involved with interval measurements will be blinded with respect to subject, treatment, recording date and time as well as planned time points of the ECGs. The staff involved with the morphological analyses will be blinded with respect to treatment. For the quality control of the measurements, certain members of the ECG evaluation team will review the entire portfolio of ECG measurements for each subject blinded to date, time, and time point.

During the time a role/function is blinded according to the table above, the randomisation schemes and medication kit lists (i.e., the treatment information) are kept restricted by the global Randomisation Team per Sponsor SOP.

4.1.5.2 Unblinding and breaking the code

As this trial will be conducted open label (FE part) / single blind (SRD part), subjects' treatment assignments will be known to investigators. Therefore, no emergency envelopes will be provided. The SAE/AESI Individual Case Safety Report (ICSR) in the safety database will be open and treatment/dosage known.

4.1.6 Packaging, labelling, and re-supply

The investigational medicinal products will be provided by BI or a designated CRO. They will be packaged and labelled in accordance with the principles of Good Manufacturing Practice (GMP).

The label will be prepared according to Regulation (EU) No. 536/2014, Annex 6, omitting certain particulars with the following justifications:

- The investigator name was omitted from the label because it is included on the Trial Identification Card (TIC), which will be issued to each trial subject.
- The "keep out of reach of children" statement was omitted from the label because the product will remain at the clinical site.

The visit number is not relevant for the label (SRD part) because there is only one visit.

For details of packing and the description of the label, refer to the ISF.

The telephone number of the sponsor and the name, address and telephone number of the trial site are provided in the subject information form. The EU Clinical Trial Number is indicated on the title page of this protocol as well as on the subject information and informed consent forms. Examples of the labels will be available in the ISF.

No re-supply is planned.

4.1.7 Storage conditions

Drug supplies will be kept in their original packaging and in a secure limited access storage area in accordance with the recommended (labelled) storage conditions. If necessary, a temperature log must be maintained to make certain that the drug supplies are stored at the correct temperature. If the storage conditions are found to be outside the specified range, the Clinical Research Associate (as provided in the list of contacts) is to be contacted immediately.

4.1.8 Drug accountability

The investigator or designee will receive the investigational drugs delivered from the sponsor when the following requirements are fulfilled:

- Approval of the clinical trial protocol by the IRB / ethics committee
- Approval/notification of the regulatory authority, e.g. competent authority
- Availability of the *curriculum vitae* of the Principal Investigator
- Availability of a signed and dated clinical trial protocol

Only authorised personnel documented in the form 'Trial Staff List' may dispense investigational drugs to trial subjects. Investigational drugs are not allowed to be used outside of this protocol.

The investigator or designee must maintain records of the product's delivery to the trial site, the inventory at the site, the use by each subject, and the disposal of unused products. These

records will include dates, quantities, batch / serial numbers, expiry ('use-by') dates, and the unique code numbers assigned to the investigational medicinal product and trial subjects. The investigator or designee will maintain records that document adequately that the subjects were provided the doses specified by the CTP and reconcile all investigational medicinal products received from the sponsor. At the time of disposal of remaining trial medication, the investigator or designee must verify that no remaining supplies are in the investigator's possession.

All unused trial medication will be disposed of locally by the trial site upon written authorisation of the Clinical Trial Leader. Receipt, usage, and disposal of trial medication must be documented on the appropriate forms. Account must be given for any discrepancies.

4.2 OTHER TREATMENTS, EMERGENCY PROCEDURES, RESTRICTIONS

4.2.1 Other treatments and emergency procedures

There are no special emergency procedures to be followed. No additional treatment is planned. However, if adverse events require treatment, the investigator can authorise symptomatic therapy. In those cases, subjects will be treated as necessary and, if required, kept under supervision at the trial site or transferred to a hospital until all results of medical evaluations are acceptable.

4.2.2 Restrictions

4.2.2.1 Restrictions regarding concomitant treatment

In principle, no concomitant therapy is allowed. This includes (re-)vaccination of any kind. All concomitant or rescue therapies will be recorded (including time of intake on trial days) on the appropriate pages of the CRF.

4.2.2.2 Restrictions on diet and life style

While admitted to the trial site, the subjects will be instructed not to consume any foods or drinks other than those provided by the staff. Standardised meals will be served at the times indicated in the [Flow Chart – SRD Part](#) and [Flow Chart – FE Part](#). No food is allowed for at least 4 h after drug intake.

From 1 h before drug intake until lunch, fluid intake is restricted to the milk served with breakfast prior to treatment T in the FE part (see Table [4.1.4: 2](#)), the water administered with the drug, and an additional 240 mL of water served at 2 h and 4 h post-dose (mandatory for all subjects).

During the days of urine collection, total fluid intake should be at least 1.5 litres and should not exceed 3.5 litres.

Grapefruits, Seville oranges (sour or bitter oranges) and their juices, and dietary supplements and products containing St. John's wort (*Hypericum perforatum*) are not permitted from 7 days before the (first) administration of trial medication until after the last PK sample of the trial is collected.

Alcoholic beverages must not be consumed from 3 days before the (first) administration of trial medication until after the last PK sample of the trial is collected.

Methylxanthine-containing drinks or foods (such as coffee, tea, cola, energy drinks, or chocolate) are not allowed from 10 h before until 24 h after administration of trial medication.

Smoking is not allowed during in-house confinement.

Excessive physical activity (such as competitive sport) should be avoided from 7 days before the first administration of trial medication until the end of trial examination.

Direct exposure to the sun or exposure to solarium radiation should be avoided during the entire trial. Trial subjects are advised to apply protective measures such as sunscreen and sunglasses while outdoors. Contraception requirements.

Subjects whose sexual partner is a WOCBP must use male contraception (sexually abstinent or use of condoms) during the study and for at least 30 days after the last dose of BI 3000202.

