Visit	Day	Planned time (relative to drug administration) (h:min)	Approximate clock time of actual day (h:min)	Event and comment	Safety laboratory ⁸	PK blood ^{10,12}	PK urine ^{10,13}	PD blood ¹⁰	12-lead ECG ⁹	Continuous ECG monitoring	Vital signs (BP, PR)	Questioning for AEs and concomitant therapy ⁶
1	-21 to -1			Screening (SCR) ¹	x ^A				x		x	
2	-3 to -1	-74:00 ⁷	06:00	Ambulatory visit	x ^{B,7}							x
	1	-1:30	06:30	Admission to trial site ²								
		-1:00	07:00		x ⁵				x ^{2,9}	x ²	x ²	x ²
		-0:45	07:15						x ^{2,9}			
		-0:30	07:30	Allocation to treatment ²	x ^{C,2}	x ²	x ²	x ²	x ^{2,9}			
		0:00	08:00	Drug administration			▲			▲		
		0:15	08:15			x						
		0:30	08:30			x			x ⁹		x	x
		0:45	08:45			x						
		1:00	09:00			x		x	x ⁹		x	x
		1:30	09:30			x ¹¹			x ⁹			
		2:00	10:00	240 mL fluid intake		x		x	x ⁹		x	x
		2:30	10:30			x						
		3:00	11:00			x			x ⁹		x	x
		4:00	12:00	240 mL fluid intake, thereafter lunch ³		x	+	x	x ⁹	▼	x	x
		5:00	13:00			x						
		6:00	14:00			x		x	x ⁹			
		7:00	15:00	Snack (voluntary) ³								
		8:00	16:00			x	+	x	x ⁹		x	x
		10:00	18:00	Dinner ³								
		12:00	20:00			x	+		x ⁹		x	x
	2	24:00	08:00	Breakfast (voluntary) ³ , discharge from trial site	x ^C	x	▼	x	x ⁹		x	x
	3	48:00	08:00	Ambulatory visit		x		x ¹⁴	x ⁹		x	x
4	4 to 14			End of study (EoS) examination ⁴	x ^D				x		x	x

- Subject must be informed and written informed consent obtained prior to starting any screening procedures. Screening procedures include physical examination, check of vital signs, 12-lead ECG and rhythm strip over at least 15 min, safety laboratory (including drug screening and infectious serology), demographics (including determination of body height and weight, smoking status and alcohol history), medical history, concomitant therapy and review of inclusion/exclusion criteria. Pharmacogenetic samples will be collected if needed.
- The time is approximate; procedures are to be performed and completed within the 3 h prior to drug administration. Allocation to treatment may be performed at any time following enrolment but must be completed prior to drug administration.
- If several actions are indicated at the same time, the intake of meals will be the last action..
- At the end of study (synonym for End of Trial), the EoS examination includes physical examination, vital signs, ECG, safety laboratory, recording of AEs, and concomitant therapies.
- Urine drug screening and alcohol breath test only

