3.3.3 Exclusion criteria

Subjects will not be allowed to participate, if any of the following general criteria apply:

1. Any finding in the medical examination (including BP, PR or ECG) deviating from normal and assessed as clinically relevant by the investigator
2. Repeated measurement of systolic blood pressure outside the range of 90 to 140 mmHg, diastolic blood pressure outside the range of 50 to 90 mmHg, or pulse rate outside the range of 50 to 90 bpm
3. Any laboratory value outside the reference range that the investigator considers to be of clinical relevance
4. Any evidence of a concomitant disease assessed as clinically relevant by the investigator
5. Gastrointestinal, hepatic, renal, respiratory, cardiovascular, metabolic, immunological or hormonal disorders

6. Cholecystectomy or other surgery of the gastrointestinal tract that could interfere with the pharmacokinetics of the trial medication (except appendectomy or simple hernia repair)
7. Diseases of the central nervous system (including but not limited to any kind of seizures or stroke), and other relevant neurological or psychiatric disorders
8. History of relevant orthostatic hypotension, fainting spells, or blackouts
9. Relevant chronic or acute infections
10. Any documented active or suspected malignancy or history of malignancy within 5 years prior to screening, except appropriately treated basal cell carcinoma of the skin
11. History of relevant allergy or hypersensitivity (including allergy to the trial medication or its excipients and including intolerance or allergy to standardised meals)
12. Use of drugs within 21 days of planned administration of trial medication that might reasonably influence the results of the trial (including drugs that cause QT/QTc interval prolongation) or vaccination of any kind within 21 days of planned administration of trial medication or any vaccination requiring re-vaccination during the course of the trial
13. Intake of an investigational drug in another clinical trial within 60 days of planned administration of investigational drug in the current trial, or concurrent participation in another clinical trial in which investigational drug is administered
14. Smoker (more than 10 cigarettes or 3 cigars or 3 pipes per day)
15. Inability to refrain from smoking on specified trial days
16. Alcohol abuse (consumption of more than 24 g per day)
17. Drug abuse or positive drug screening

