18. Blood donation of more than 100 mL within 30 days of planned administration of trial medication or intended blood donation during the trial
19. Intention to perform excessive physical activities within one week prior to the administration of trial medication or during the trial
20. Inability to comply with the dietary regimen of the trial site
21. A marked prolongation of QT/QTc interval (such as QTc intervals that are repeatedly greater than 450 ms) or any other relevant ECG finding at screening
22. A history of additional risk factors for *Torsade de Pointes* (such as heart failure, hypokalaemia, or family history of Long QT Syndrome)
23. Subject is assessed as unsuitable for inclusion by the investigator, for instance, because the subject is not considered able to understand and comply with study requirements, or has a condition that would not allow safe participation in the study
24. Prior history of jaundice excluding neonatal jaundice
25. ALT (alanine transaminase) or AST (aspartate transaminase) or serum creatinine above upper limit of normal range at screening examination, confirmed by a repeat test
26. Total bilirubin above 1.5 upper limit of normal range at screening examination, confirmed by a repeat test.

27. Male subjects with WOCBP partner who are unwilling to use male contraception (condom or sexual abstinence) from time point of administration of trial medication until 30 days thereafter

For restrictions of the trial, refer to Section [4.2.2](#).

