6.2.2 Treatment periods

SRD part

Each subject will receive one single dose of trial medication (BI 3000202 or placebo) at Visit 2. Trial subjects will be admitted to the trial site in the morning of Day 1 and kept under close medical surveillance for at least 24 h following drug administration. The subjects will then be allowed to leave the trial site after formal assessment and confirmation of their fitness by the investigator or [REDACTED].

FE part

Each subject will receive a single dose of BI 3000202 on Day 1 of Visits 2 and 3. Drug administrations will be separated by a washout period of at least 3 days (ref. [Flow Chart – FE Part](#)). Trial subjects will be admitted to the trial site in the evening of Day -1 and kept under close medical surveillance for at least 24 h following drug administration in each period. The subjects will then be allowed to leave the trial site after formal assessment and confirmation of their fitness by the investigator or [REDACTED].

Both parts

Trial medication will be [REDACTED] supervision of the investigator or [REDACTED] designee. Details on treatments and procedures of administration are described in Section [4.1.4](#).

For details on time points and procedures for collection of plasma and urine samples for PK and biomarker analysis, refer to [Flow Chart – SRD Part](#) and Flow Chart – FE Part, Sections [5.3.2](#) and [5.4.2](#).

The safety measurements performed during the treatment periods are specified in Section [5.2](#) of this protocol. AEs and concomitant therapy will be assessed continuously from the time of the subject's written informed consent until the end of trial examination.

For details on times of all other trial procedures, refer to the Flow Chart – SRD Part and Flow Chart – FE Part.

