## 6.7 BASELINE, TIME WINDOWS AND CALCULATED VISITS

[REDACTED]

For all analyses (except for analyses of ECG variables), the baseline value is defined as the last measurement prior to the drug administration (in each treatment period for FE part).

There will be a centralised evaluation of the 12-lead ECG recordings at the time points and for the ECG recordings specified in [Table 6.7: 1](#) below. This will be performed for the SRD part only.

Three triplicate ECGs will be recorded as the baseline before the first drug administration, but only the first ECG of each of the 3 baseline triplicates will be transferred to the database. At all other time points, 1 triplicate ECG will be recorded, but only the first single ECG of the triplicate will be transferred to the database. The baseline value of an ECG variable is defined as the mean of the ECG variable values prior to drug administration.

[REDACTED]

Unscheduled measurements of laboratory data and vital signs data will be assumed to be repeat measurements of the most recent scheduled measurement (e.g. for follow-up or

confirmation of a particular value). Therefore, unscheduled measurements will be assigned to the planned time point of the previous scheduled measurement.

Table 6.7: 1 Time schedule of 12-lead ECG recordings

Visit	Day	Planned time (hh:mm) (relative to drug administration)	Study phase	Central evaluation
1	-21 to -1		Screening	NA
2	1	-01:00	Baseline	first ECG of each of the 3 triplicate baselines
		-00:45		
		-00:30		
		00:30	On-treatment	first single ECG of the triplicate
		01:00		
		01:30		
		02:00		
		03:00		
		04:00		
		06:00		
		08:00		
		12:00		
	2	24:00		
	3	48:00		NA
4	4 to 14		End-of-study examination	NA

Time windows are defined in Section 6.1 of the CTP. Adherence to time windows will be checked at the RPM.

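### In the SRD part the smoking ban starts only at admission, 90 min before dosing, so baseline heart rate, blood pressure and uncorrected QT may be measured soon after a cigarette while readings to 24 h are smoke-free (minor)

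*Protocol*

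**What the plan says.** - **Who may enter.** Protocol 3.3.3, criterion 14, excludes "Smoker (more than 10 cigarettes or 3 cigars or 3 pipes per day"). Lighter smokers are eligible. Criterion 15 excludes "Inability to refrain from smoking on specified trial days" but does not list the days. The section closes with "For restrictions of the trial, refer to Section" 4.2.2.
- **The rule itself.** Section 4.2.2.2 contains one sentence on smoking: "Smoking is not allowed during in-house confinement". It gives no period of abstinence before admission.
- **When confinement starts.** For the SRD part, Protocol 6.2.2 states "Trial subjects will be admitted to the trial site in the morning of Day 1". The SRD flow chart places this 90 min before dosing ("1:30 06:30 Admission to trial site", with a minus sign before the time). FE subjects come in the evening before, at -14:00.
- **When baseline is taken.** In the SRD flow chart, pre-dose vital signs are at -1:00 and baseline ECGs at -1:00, -0:45 and -0:30. Footnote 2 calls these times approximate.
- **How baseline is used.** SAP 6.7 says "The baseline value of an ECG variable is defined as the mean of the ECG variable values prior to drug administration". For vital signs it takes the last pre-dose value.
- **A rule of a different kind in the same section.** Methylxanthine-containing food and drink "are not allowed from 10 h before until 24 h after administration of trial medication", whatever the admission time.

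**The concern.** A change from baseline is interpretable when baseline and follow-up are measured under like conditions. Here a subject who follows the rules can smoke on the way in, have his baseline recorded, and then abstain for 24 h. If nicotine raises resting heart rate and blood pressure, his baseline is too high. Heart rate then appears to fall and uncorrected QT to lengthen after dosing, and a true rise in heart rate is understated.

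These readings matter in the SRD part. QT/QTc prolongation is the first compound risk in Protocol Table 1.4.2: 1. Section 1.3.3 mentions using SRD exposures to support waiving a thorough QT trial, and changes from baseline in HR and QT are summarised under SAP 7.8.4. The problem also cannot be repaired later. Smoking status is a screening item, the Day 1 check is a urine drug screen and alcohol breath test only, the drug panel in Table 5.2.3: 2 has no nicotine marker, and no section asks for the time of the last cigarette.

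**Working it through.** **Step 1: timing, from the two flow charts and SAP Table 6.7: 1.** Smoke-free time guaranteed by the rule = 90 min minus the reading's pre-dose time (SRD part).

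| Reading | Calculation | Guaranteed abstinence |
|---|---|---|
| Vital signs and first baseline ECG, -1:00 | 90 - 60 | 30 min |
| Second baseline ECG, -0:45 | 90 - 45 | 45 min |
| Third baseline ECG, -0:30 | 90 - 30 | 60 min |
| ECG baseline (mean of three) | (30 + 45 + 60)/3 | 45 min on average |
| First on-treatment ECG, 0:30 | 90 + 30 | 2 h |
| Last centrally evaluated ECG, 24:00 | 1.5 h + 24 h | 25.5 h |
| FE baseline, -1:00 | 14 h - 1 h | 13 h (9 h if FE admission procedures end at -10:00) |

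These are nominal values. Because the pre-dose times are approximate, even 30 min is not assured. The 48 h SRD readings fall after discharge, when smoking is allowed again, but the 48 h ECG is not centrally evaluated.

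**Step 2: possible size.** The documents give no nicotine effect and no smoking prevalence. Assumption: a recent cigarette raises resting heart rate by 5 to 15 bpm, with no decay before the readings. Hold QTcF at 400 ms and use the Fridericia relation QT = QTcF × (60/HR)^(1/3).

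- HR 75: 400 × 0.800^(1/3) = 371.3 ms
- HR 70: 400 × 0.857^(1/3) = 380.0 ms, a difference of about 9 ms
- HR 65: 400 × 0.923^(1/3) = 389.5 ms, a difference of about 18 ms
- HR 60: 400 × 1^(1/3) = 400.0 ms, a difference of about 29 ms

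The shift in the mean of 6 active subjects, if k of them smoked before admission (10 bpm and 18 ms each), is k/6 times the individual shift:

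- k = 1: -1.7 bpm, +3 ms
- k = 2: -3.3 bpm, +6 ms
- k = 3: -5.0 bpm, +9 ms

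Against pooled placebo the bias is the individual shift × (fraction of active subjects who smoked - fraction of placebo subjects who smoked). It is zero if the fractions are equal.

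**Step 3: thresholds in SAP 5.3.1 and Protocol 3.3.4.3.**

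- *QT change above 60 ms.* The largest shift above is 29 ms. At the eligibility limits (QTcF 450 ms in criterion 21, pulse rate 50 bpm in criterion 2), a 15 bpm effect gives 450 × [(60/50)^(1/3) - (60/65)^(1/3)] = 478.2 - 438.2 = 40 ms. This is still below 60 ms, with absolute QT below 500 ms.
- *HR notable finding.* This needs a fall of at least 25% together with HR below 50, or a rise of at least 25% together with HR above 100. A change from 75 to 60 bpm is -15/75 = -20%, ending at 60. For any smoke-free rate of 50 bpm or more, the below-50 condition fails.
- *QT stopping criterion.* This needs a QTc increase above 60 ms with QT or QTc above 500 ms, confirmed by a repeat ECG. QTcF was held fixed, so its increase here is zero.

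**The case against.** The best defence is that criterion 15 already covers the dosing morning. Protocol Section 6 describes the treatment period as 3 trial days, and a site could take Day 1 as smoke-free. That is a possible reading, but nothing states it, and the section to which the reader is sent mentions confinement only. The two passages need to be reconciled in either case.

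A second argument is that the comparison with pooled placebo absorbs the shift, because placebo subjects follow the same rule. This holds for a shift common to all groups. It does not hold if smokers are unevenly spread over groups of 6, which are filled by subjects' availability (Protocol 4.1.3). Smoking status is collected at screening, so an imbalance in status could be examined, but not who smoked that morning.

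A third is that the size is assumed. That stands: the heart-rate effect and the number of smokers are illustrations, the full effect is applied without decay, and the timing supposes a cigarette just before admission. The protocol also gives no reason for its methylxanthine window, so 10 h has no specific support for nicotine.

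A reader might infer that the QTcF read-out or dose escalation is at risk. The documents do not support this. The calculation holds QTcF constant, so it shows no QTcF bias, and on-site cardiac safety assessment relies on QT and QTcF (Protocol 5.2.4.1). A concentration-ECG analysis is planned, but its SAP details are not visible, so its handling of baseline cannot be judged.

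**Conclusion.** The point holds as a minor one. In the SRD part, the stated rule allows baseline and on-treatment readings to be taken under different smoking conditions. This can bias change from baseline in heart rate, blood pressure and uncorrected QT, with no record from which to correct it. The timing follows directly from the documents. The size does not: about 9 to 29 ms of uncorrected QT rests on the assumed 5 to 15 bpm, a QTcF of 400 ms and a starting rate of 75 bpm, and no figure is offered for blood pressure. It would be wrong to conclude that smoking alone would produce QT changes above 60 ms, HR notable findings or a stop in escalation, since none of those limits is reached in Step 3. The SRD primary endpoint is drug-related adverse events and the safety analyses are descriptive, which also keeps the grade low.

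**What to change.** In Protocol 4.2.2.2, start the restriction on smoking and other nicotine use at a stated time before dosing that does not depend on admission, and continue it until discharge. The 10 h window already used for methylxanthines is a convenient choice. In 3.3.3, have criterion 15 refer to that window in place of its unnamed days.

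The cost is one sentence in each section, with no extra visit or sample. The drawback is that in the SRD part abstinence before admission would be self-reported, as the overnight fast and caffeine restriction already are.
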